#### 7.7.1.1. Adverse Events Associated with COVID-19

The selection of AEs associated with COVID-19 will be based on the MedDRA MSSO list of PTs. The following will be summarized:

- TEAEs associated with COVID-19, by SOC and PT
- Grade  $\geq$ 3 TEAEs associated with COVID-19, by SOC and PT
- Serious TEAEs associated with COVID-19, by SOC and PT
- TEAEs associated with COVID-19 leading to discontinuation of study drug, by SOC and PT
- TEAEs associated with COVID-19 leading to interruption of study drug, by SOC and PT
- TEAEs associated with COVID-19 leading to dose reduction, by SOC and PT
- TEAEs associated with COVID-19 leading to death, by SOC and PT

#### 7.7.2. Death

The frequency of subjects who died, along with the cause of death, will be summarized for the following categories:

- On-treatment death: Deaths during the on-treatment period
- Post-treatment death: Deaths after the end of the on-treatment period

• Overall: All deaths

In addition, deaths related to COVID-19 will be summarized.

Deaths for all screened subjects will be provided in a by-subject listing.

### 7.7.3. Clinical Laboratory Data

Clinical laboratory test results will be expressed in SI units. For chemistry and hematology laboratory tests, the actual values and the changes from baseline will be summarized by study visit.

For each laboratory test performed in the study, a by-subject listing of laboratory test results will be presented with the corresponding CTCAE grades (if applicable), laboratory normal ranges, and flags for values below lower limit of normal (LLN) or above upper limit of normal (ULN).

### Parameters with CTCAE grades available:

Clinical laboratory test results will be graded according to CTCAE v4.03 as applicable. Grading will be derived based on the numerical thresholds defined by the CTCAE criteria. Non-numerical qualifiers will not be taken into consideration in the derivation of CTCAE grading.

Laboratory test results classified according to CTCAE will be described using the worst grade. For parameters graded with 2 separate toxicity criteria, such as potassium (hypokalemia/hyperkalemia), the toxicities will be summarized separately. Low direction toxicity (eg, hypokalemia) grades at baseline and postbaseline will be set to 0 when the variables are derived for summarizing high direction toxicity (eg, hyperkalemia), and vice versa.

The frequency of subjects with laboratory toxicities during the on-treatment period will be tabulated as follows. The denominator used to calculate percentages for each laboratory test is the number of subjects evaluable for CTCAE grading for that parameter (ie, those subjects for whom a Grade of 0, 1, 2, 3 or 4 can be derived).

- The summary of laboratory parameters by CTCAE grade will include the number and percentage of subjects with Grade 1, 2, 3, 4; Grade 3-4; and Any Grade (Grades 1-4) during the on-treatment period. The highest CTCAE grade during the on-treatment period is considered the worst grade.
- The shift table will summarize baseline CTCAE grade versus worst CTCAE grade during the on-treatment period. The highest CTCAE grade during the on-treatment period is considered the worst grade.
- Newly occurring or worsening laboratory abnormalities (Any Grade, Grade 3-4) during the on-treatment period will also be summarized.

#### Parameters with CTCAE grades not available:

Results of laboratory tests that are not part of CTCAE will be presented according to the following categories: below the LLN, within normal limits, and above the ULN according to the laboratory normal ranges.

Shift tables will display the frequency of subjects with shifts from baseline missing, <LLN, normal, or >ULN to each of <LLN, normal or >ULN during the on-treatment period.

## 7.7.3.1. Hematology

For **WBC differential counts** [total neutrophil (including bands), lymphocyte, monocyte, eosinophil, and basophil counts], the absolute value will be used when reported. When only percentages are available (relevant primarily for neutrophils and lymphocytes, because the CTCAE grading is based on the absolute counts), the absolute value is derived as follows:

[figure not shown]
Derived differential absolute count=(WBC count)×(Differential % value/100)

[figure not shown]
If the range for the differential absolute count is not available (ie, the range is only available for the percentage) then Grade 1 will be attributed as follows:

- Lymphocyte count decreased:
  - Derived absolute count does not meet Grade 2-4 criteria, and
  - % value <% LLN value, and
  - Derived absolute count  $\geq 800/mm^3$
- Neutrophil count decreased:
  - Derived absolute count does not meet Grade 2-4 criteria, and
  - % value<% LLN value, and
  - Derived absolute count  $\geq 1,500/\text{mm}^3$

## 7.7.3.2. Chemistry

**Liver function tests**: Alanine aminotransferase (ALT), aspartate aminotransferase (AST), alkaline phosphatase (ALP), and total bilirubin are used to assess possible drug-induced liver toxicity. The ratios of test result to ULN will be calculated and categorized for these parameters during the on-treatment period.

#### 7.7.3.3. Sex Hormone Tests

For sex hormone test results, shift tables will display the frequency of subjects with shifts from baseline missing, < LLN, normal, > ULN to each of < LLN, normal or > ULN during the on-treatment period.

In addition, individual longitudinal plots will be provided for each sex hormone by sex.

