8.6.3. Clinical Laboratory Safety Assessments

Study-required clinical laboratory assessment samples will be analyzed by a central laboratory. Local laboratory analysis is allowed, at the discretion of the Investigator, if faster turnaround time is required to support clinical decision-making. If samples for local laboratory analysis are collected, the study-required samples for central laboratory analysis must also be collected at the same time. Subjects will be monitored for potential aromatase inhibition by assessments of sex hormone levels.

Clinical laboratory safety assessment parameters are listed in Table 10.

Assessment	Parameters
Hematology	• Complete blood count (Hb, HCT, MCHC, MCH, MCV, RBC count, nucleated RBCs, RDW-CV, % reticulocyte count, absolute reticulocyte count, and platelet count) with WBC count and differential (neutrophils, basophils, eosinophils, lymphocytes, and monocytes)
Clinical chemistry	• Albumin, BUN or urea, total calcium, CO ₂ or bicarbonate, chloride, creatinine, magnesium, phosphorus, potassium, sodium, total protein, and uric acid
Liver tests	 ALP, ALT/SGPT, AST/SGOT, and bilirubin (direct/conjugated, indirect/unconjugated, and total) LDH
Coagulation tests	Fibrinogen, aPTT, and INR
Lipid panel	Nonfasting HDL-C, LDL-C, total cholesterol, and triglycerides
Sex hormones	Nonfasting estradiol, estrone, and testosterone (total and free)
Screening virology	• HBsAg, HCV Ab (positive results for HCV Ab testing require confirmation by a test for HCV-RNA), HIV-1 Ab, and HIV-2 Ab
Screening FSH and serum hCG	• FSH (for women in the absence of 12 months of amenorrhea to confirm non–reproductive potential) and a serum (hCG) pregnancy (for WOCBP)

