10.4.4.2. Clinical Laboratory Assessments

The actual values and the changes from baseline will be summarized by study visit for clinical laboratory tests.

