#### **Analysis Visit Windows**

For the evaluation of efficacy endpoints (Section 7.6),

and BMD by DXA scan (Section 7.7.5), the analysis visit windows will be derived based on the target study day for the scheduled visits as follows. Note that based on the schedule of assessments, a Week 4 Visit, for example, will have a target study day of  $1+(4\times7)=29$ .

For the Double-blind Period:

- Visit windows will be implemented for scheduled visits after study day 1 (ie, starting at Week 4 through the end of the Double-blind Period on Week 24).
- For analysis visit(n):
  - Start day of visit window =1+end day of window for visit(n-1). If n=1, start day of the visit window is study day 2
  - End day of visit window = [(target day for analysis visit(n) + target day for analysis visit(n+1))/2]-1 for Week < 24. The end day of visit window for Week 24 is the end of the Double-blind Period

  - Not applicable to DXA scan results which are only scheduled in the OLE Period.

For the OLE Period:

• Visit windows will be implemented for all scheduled visits after the first dose of mitapivat in the OLE Period. Week 288 is the last scheduled visit in the OLE Period.

- For analysis visit(n):
  - Start day of visit window = 1+ end day of window for visit(n-1). If n=1, start day of the visit is the day after the first dose of mitapivat in the OLE Period.
  - End day of visit window = [(target day for analysis visit(n) + target day for analysis visit(n+1))/2]-1 for Week < 288. The end day of visit window for Week 288 is the EOS date.

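### The SAP drops the by-visit values and changes that the protocol calls for on sex hormones, so a within-range change against placebo is not quantified by arm

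*SAP*

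**What the plan says.** Protocol 8.6.3 gives the purpose of the tests: "Subjects will be monitored for potential aromatase inhibition by assessments of sex hormone levels". Its Table 10 lists estradiol, estrone and testosterone (total and free) as clinical laboratory safety tests, on a row separate from clinical chemistry. Protocol 10.4.4.2 then states the analysis without excepting any test: "The actual values and the changes from baseline will be summarized by study visit for clinical laboratory tests".

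SAP 7.7.3 is narrower: "For chemistry and hematology laboratory tests, the actual values and the changes from baseline will be summarized by study visit". Sex hormones have their own section, 7.7.3.3, apart from 7.7.3.2 (Chemistry). That section plans two outputs. The first is tabular: "For sex hormone test results, shift tables will display the frequency of subjects with shifts from baseline missing", below LLN, normal or above ULN, to each of the last three during the on-treatment period. The second is graphical: "In addition, individual longitudinal plots will be provided for each sex hormone by sex". SAP 7.7.3 also provides a listing: "For each laboratory test performed in the study, a by-subject listing of laboratory test results will be presented", with normal ranges and flags.

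Protocol Table 1 schedules sex hormones on Day 1 and at Weeks 12 and 24 of the Double-blind Period. Bone mineral density, the other measure the protocol ties to aromatase inhibition (8.6.4), has no post-baseline scan in that period. The SAP's visit-window rules say so: "Not applicable to DXA scan results which are only scheduled in the OLE Period".

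**The concern.** The protocol promises a numerical summary by visit, and the SAP as written does not produce it for these tests. SAP section 2 allows the SAP to modify the protocol's plans, but no reason is given here, and the omission reads like an oversight. DXA results (SAP 7.7.5) and vital signs (SAP 7.7.4) both get summaries by arm and visit.

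A shift table counts only subjects who cross a limit. If mitapivat moved a hormone by a moderate amount inside the normal range, the table could look much the same in both arms. The plots would show up to about 171 individual lines, and the listing would show the values, but nothing would state the size of the difference from placebo. That difference is available only from the Double-blind Period, because everyone who continues into the extension receives mitapivat.

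**Working it through.** **Text comparison**

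1. Are sex hormones clinical laboratory tests under the protocol? Yes, by Table 10.
2. Does Protocol 10.4.4.2 exempt them from the by-visit summary? No.
3. Could they be read into chemistry in SAP 7.7.3? Not naturally. Protocol Table 10 and the SAP both list them apart from chemistry.
4. Does SAP 7.7.3.3 restore the summary? No. Its shift table has the same form as the generic one for parameters without CTCAE grades, so the section adds only the plots.

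**Illustration of size**

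The documents give no sex hormone figure to reproduce, so every input except the arm sizes is an assumption.

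- Arm sizes: 114 mitapivat and 57 placebo (SAP 6.2.1).
- Normal range: holds the central 95% of subjects, so 2.5% of placebo values lie below LLN.
- True effect: a fall of δ SD on mitapivat. A rise across ULN gives the same figures by symmetry.
- SD of change: equal to the between-subject SD, that is, a test-retest correlation of 0.5.
- One visit.
- Sex split: 60% women. That gives 0.6 × 114 ≈ 68 and 0.6 × 57 ≈ 34 women, leaving 46 and 23 men.

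Share below LLN on mitapivat = Φ(−1.96 + δ). Power of the shift-table comparison is the exact power of Fisher's test, two-sided 0.05, 114 vs 57. Power for mean change is that of the two-sample t test with noncentrality δ × √(n₁n₂/(n₁+n₂)). In the smaller sex group this is δ × √(46 × 23/69) = 3.92δ on 67 degrees of freedom.

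| Fall δ (SD) | Below LLN, mitapivat vs placebo | Fisher, all 171 | Mean change, 46 vs 23 |
|---|---|---|---|
| 0.25 | 4.4% vs 2.5% | 2% | 16% |
| 0.5 | 7.2% vs 2.5% | 13% | 49% |
| 0.75 | 11.3% vs 2.5% | 46% | 82% |
| 1.0 | 16.9% vs 2.5% | 84% | 97% |

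At δ = 0.5 the expected counts below LLN are 114 × 0.072 ≈ 8 and 57 × 0.025 ≈ 1.4. For the same fall, mean change has about 65% power in women (68 vs 34).

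The table sets the shift comparison in everyone against mean change in the smaller group, which favours the shift table. Like for like within one sex (57 vs 28, correlation 0.5 to 0.8, δ = 0.5, simulated on new values below LLN), the shift comparison has about 1% power and mean change 58% to 93%.

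**Sensitivity of the shift-table figures**

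- Counting a value below LLN at either Week 12 or Week 24 (between-visit correlation 0.5 to 0.8) raises Fisher power to 5–6%, 24–30%, 64–73% and 94–98% across the four falls.
- If 10% to 30% of subjects would lie below LLN without treatment, single-visit power at δ = 0.5 is 45% to 65%.

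**The case against.** A reader might infer that sex hormones are reduced to shift tables and that a within-range effect would go undetected. The documents do not support this. SAP 7.7.3.3 also plans longitudinal plots of each hormone by sex, and SAP 7.7.3 lists every value with its range, so such a change can be seen. What is missing is its size by arm.

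A reader might also infer that the shift tables pool men and women. That comes from silence. The section names no split by sex for the tables and no pooling, and the documents do not say whether the laboratory ranges are sex-specific. If they are, each subject is already classified against limits for their own sex.

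It would also be too strong to call the hormones the only randomised evidence on aromatase inhibition, because double-blind adverse events are summarised by arm (SAP 7.7 and 7.7.1). The narrower statement holds: they are the only hormone or bone measure with a concurrent placebo arm.

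The power figures are open to fair criticism. No hypothesis test is planned for safety data, the effect sizes are assumed, and a large shift would show in the shift table. Counting both visits, or a higher background share below LLN, narrows the gap. At 0.5 SD the higher background share can bring the whole-sample shift table level with, or above, mean change in the smaller sex group. The figures therefore show how much information the categories can lose, and they do not predict this trial's result. None of this removes the mismatch between Protocol 10.4.4.2 and SAP 7.7.3.

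**Conclusion.** The point stands as a protocol–SAP inconsistency with a practical consequence. Followed as written, the SAP gives no numerical summary by arm and visit of sex hormone values or changes, although the protocol calls for one and names the safety question these tests serve. A change within the normal range would be shown in individual plots and listings but not quantified against placebo.

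Under the stated assumptions the loss is greatest for moderate changes (13% against 49% power at 0.5 SD, 46% against 82% at 0.75 SD) and small for changes near 1.0 SD. The direction rests on dichotomising a continuous measure. The size rests on the assumed reference range, correlation, sex split and single visit. The textual finding needs none of these assumptions. The change should be made, but it does not touch the primary or key secondary analyses.

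**What to change.** In SAP 7.7.3 or 7.7.3.3, add actual values and change from baseline for estradiol, estrone, and free and total testosterone, by treatment arm and visit within each sex, covering Weeks 12 and 24 of the Double-blind Period. State that the shift tables are presented by sex. A descriptive difference between arms with a 95% CI may be added; it goes beyond what the protocol asks. A separate display of subjects taking exogenous sex hormones is optional. If the omission was deliberate, the SAP should give the reason.

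The cost is SAP wording and one set of tables. The samples are already scheduled and sex is already recorded, so nothing in the conduct of the trial changes. The drawback is smaller groups per table, down to about 46 and 23 for one sex under the assumed split.

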#### 7.7.3.4. Pregnancy Tests

Pregnancy test results will be presented in a by-subject listing.

#### 7.7.4. Vital Signs and Physical Measurements

For all physical measurements and vital sign assessments (height, weight, BMI, systolic blood pressure, diastolic blood pressure, pulse rate, temperature) the actual values and the changes from baseline will be summarized by treatment arm and study visit. Change from baseline does not apply to height.

Vital signs and physical measurements will be presented in a by-subject listing.

#### 7.7.5. Dual-Energy X-ray Absorptiometry Scans

Results from bone mineral density on DXA scan (BMD and their T-scores and Z-scores) will be summarized by treatment arm and study visit, for each location.

In addition, shift tables will summarize the frequency of subjects with shifts from baseline T-scores missing,  $\leq -2.5$ ,  $\geq -2.5$ ,  $\geq -1.0$  to worst T-score  $\leq -2.5$ ,  $\geq -2.5$ ,  $\geq -1.0$  during the on-treatment period, by location and across the two locations.

## 7.7.6. Electrocardiograms

ECGs are collected during the screening period only and will be presented in a by-subject listing.

## 7.8. Pharmacokinetic Analyses

Only data from subjects in the mitapivat arm will be included in summary tables and plots. If a subject randomized to placebo receives at least 1 dose of mitapivat and has a PK concentration  $\geq$ LLQ, the data will be listed but will be excluded from the summary tables and plots.

All listings, summaries and plots will be presented by treatment arm based on the PK analysis set.

Concentrations <LLQ will be set to 0 for summary tables and plots with the following exceptions:

- Concentrations <LLQ between 2 quantifiable concentrations will be set to missing.
- Concentrations <LLQ following the last quantifiable concentration in a profile will be set to missing.

The following data will be excluded from summary tables and plots, unless otherwise specified:

- Pre-dose samples collected post-dose
- Post-dose samples collected pre-dose
- Concentrations >5% of Cmax, for sample collected before the first dose of mitapivat
- Multiple samples collected at the same actual time point
- Samples not collected within the protocol-specified sampling windows will be excluded from the analysis but will be included in by-subject concentration-time plots.

In addition, concentrations  $\geq$ LLQ following 2 or more consecutive concentrations  $\leq$ LLQ and samples not collected within the scheduled visit window will be flagged in listings. The decision as to whether these will be included or excluded in whole or in part from the analyses will be made by the unblinded clinical pharmacologist before the study is unblinded for the analysis of the primary endpoint.

## 7.8.1. Concentration-Time Data

PK concentrations will be summarized by treatment arm, study visit and nominal time point. All the concentration-time data will be listed.

Arithmetic mean  $(\pm SD)$  of PK concentrations associated with the intensive PK sampling collection visit (Week 20), will be plotted vs nominal sampling time on both linear and log-linear scales.

By-subject PK concentrations associated with the intensive PK sampling collection visit will be plotted vs actual sampling time on both linear and log-linear scales (Week 20) by treatment arm.

By-subject PK concentrations associated with sparse PK sampling collection visits (pre-dose on Day 1 and Week 12) will be plotted vs visit using box plots. The lower and upper boundaries of the box correspond to the interquartile range (IQR). The solid line represents the median value. The whiskers represent the minimum or maximum values within 1.5×IQR.

## 7.8.2. Pharmacokinetic Parameters

Concentration-time data associated with the intensive PK sampling collection visit (Week 20) will be used to derive the PK parameters defined in Table 6 using noncompartmental analysis methodology (Gabrielsson J and Weiner D, 2016) in PhoenixTM WinNonlin® version 8.2 or later. The derivations will be based on the actual sampling time points calculated relative to the actual time of the most recent administration of mitapivat.

PK parameters will be listed and summarized by treatment arm and study visit. AUC0-last and  $T_{last}$  will be reported in the listings, but not included in the table summary if  $T_{last} < 6.5h$  or  $T_{last} > 7.5h$ .

Parameter	Description
AUC 0-last	Area under the concentration-time curve from time "0" to $T_{last}$ on dosing day, calculated using the linear-log trapezoidal rule
T last	Time of the last quantifiable concentration
C max	Maximum observed concentration.
T max	Time of maximum observed concentration
C last	Last quantifiable concentration after a single dose or within the dosing interval (tau) for multiple doses

 Table 6:
 Pharmacokinetic Parameters of Mitapivat in Plasma

# 7.9. Pharmacodynamic Analyses

All listings, summaries and plots for PD data will be presented by treatment arm based on the PD analysis set. Concentrations <LLQ will be set to missing.

The following data will be excluded from summary tables and plots, unless otherwise specified:

- Pre-dose blood samples collected post-dose
- Post-dose blood samples collected pre-dose
- Multiple samples collected at the same actual time point
- Samples not collected within the protocol-specified sampling windows

## 7.9.1. Whole Blood Concentrations of 2,3-DPG and ATP

Whole blood concentrations of 2,3-DPG and ATP, and their change from baseline and percent change from baseline will be summarized by treatment arm and study visit. Individual data will be listed.

Whole blood concentrations of 2,3-DPG and ATP measured on Week 20 will be used to derive the PD parameters defined in Table 7. The PD parameters will be listed and summarized by treatment arm.

Table 7:	Pharmacodynamic Parameters of Whole Blood Concentrations of 2,3-
	DPG and ATP

Parameters	Description
В	Baseline value as defined in Section 6.3.4
AUC_Above_B 0-7	Area of the response curve that is above the baseline value from time point zero (pre-dose) up to 7 hours (nominal time), using the linear trapezoid rule
AUC_Below_B 0-7	Area of the response curve that is below the baseline value from time point zero (pre-dose) up to 7 hours (nominal time), using the linear trapezoid rule.
AUC_Net_B 0-7	Net area of the response curve above and below the baseline value, calculated as AUC_Above_ $B_{0.7}$ - AUC_Below_ $B_{0.7}$
R max	Maximum observed response value over 7 hours post-dose
BR max	Maximum change from baseline value over 7 hours post-dose, calculated as $R_{max}$ - B
%BR max	Maximum percent change from baseline value over 7 hours post-dose, calculated as $(R_{max}$ - B) / B $\times$ 100
R min	Minimum observed response value over 7 hours post-dose
BR min	Minimum change from baseline value over 7 hours post-dose, calculated as $R_{min}$ - B
%BR min	Minimum percent change from baseline value over 7 hours post-dose, calculated as $(R_{min}$ - B) / B $\times$ 100
T max	Time of observed R max
T min	Time of observed R min

